**Table 2 Potential Reasons for Exclusion From an Analysis Set**

Reason for Exclusion	(Potentially) Leading to Exclusion From
Informed consent date missing	Screened, ITT, mITT, Safety, PK, CCI
No eligibility assessment	Screened, ITT, mITT, Safety, PK, CCI

Reason for Exclusion	(Potentially) Leading to Exclusion From
Not randomized	ITT, mITT, Safety, PK, CC
Not treated with IP	mITT, Safety, PK, CC
No blood sample available for CSL312 concentration measurement after CSL312 administration	PK
No blood sample available for the analysis of CCI	CCI

The following summaries for number and percentage of subjects will be provided by treatment and total using the Screened Analysis Set:

- Number and percentage of subjects in each of the analysis sets described in Section 6;
- Inclusion and exclusion criteria violations;
- Reasons for exclusion from an analysis set.

The following by-subject listings will be provided based on the Screened Analysis Set:

- Inclusion and exclusion criteria violations;
- All other protocol deviations;
- Subject assignment to analysis sets and reasons for exclusion.

### 9.3 Demographic and Baseline Characteristics

Descriptive statistics as specified in Section 7 will be provided for continuous variables, number and percentage of subjects for categorical variables.

BMI ( $\text{kg}/\text{m}^2$ ) will be calculated as body weight (kg) / height (m).

Number of pack-years = (packs smoked per day) \* (years as a smoker)  
= number of cigarettes per day/20 \* duration of smoking (years).

Duration of smoking will be derived from start year of smoking and year of randomization for current smokers and using the stop year of smoking for former smokers.

Comorbidity will be defined as indication for the presence of:

- hypertension;
- diabetes or;
- obesity, defined as BMI  $\geq$  30.

For each subject, the presence and type of the above comorbidities will be identified. BMI will be used to assess obesity. The preferred terms entered for diabetes and hypertension in the medical history CRF page will be used to assess the comorbidity factors. CSL will provide a list of preferred terms indicative for diabetes or hypertension.

The following summaries will be provided by treatment and total for the ITT and the mITT Analysis Set.

- Demographic characteristics (age, race, ethnicity, sex, height, body weight, and BMI at Screening). In addition to summarization as a continuous variable, age will also be categorized and summarized by the categories given in Section 8.2.7.2;
- Disease history (Positive SARS-CoV-2 test, time since onset of symptoms relative to randomization, time since admission to hospital relative to randomization, time since admission to ICU relative to randomization, chest-CT or chest-X-ray [yes, no], signs of interstitial pneumonia [yes, no]);
- Smoking status and pack years of cigarettes for current and former smokers;
- Comorbidity factors (yes, no) and type of comorbidity (hypertension, diabetes, obesity);
- Medical history (coded using the Medical Dictionary for Regulatory Activities [MedDRA] – MedDRA version will be provided in the output) will be presented by System Organ Class and Preferred Term –medical history terms with end date / evidence for end date before informed consent date will be included;
- Concomitant diseases –medical history terms with end date / evidence for end date on or after informed consent date will be included.

The following by-subject listings will be provided based on the ITT Analysis Set:

- Demographics and baseline characteristics;
- Disease history (SARS-CoV-2 CRF page, chest-CT and chest-X-ray CRF page);
- Smoking status, pack-years of cigarettes, and comorbidity factors;
- Medical history and concomitant diseases;
- Reproductive system findings, pregnancy tests, and contraception in man.

#### 9.4 Prior/Concomitant Medications and Procedures

Prior/concomitant medications will be coded using the World Health Organization Drug Dictionary. The version will be provided in the output tables and listings.

The reported medication will be classified as ‘Prior’, ‘Prior and Concomitant’ or ‘Concomitant Only’:

- ‘Prior’: if the subject has not taken any IP; or if the medication end date is before IP start date. If the medication end date is partially missing, the medication will only be assigned to ‘Prior’ if the partial date gives clear evidence that the medication stopped before IP start;
- ‘Prior and Concomitant’: if the medication is not classified as ‘Prior’ or as ‘Concomitant Only’;
- ‘Concomitant Only’: if the medication started on or after IP start date. If the medication start or end date are partially missing, the medication will only be assigned to ‘Concomitant Only’ if the partial dates give clear evidence that the medication started on or after IP start.

Concomitant medications, i.e., medications classified as ‘Concomitant Only’ or ‘Prior and Concomitant’, will be summarized for the ITT Analysis Set by treatment and total showing the number and percentage of subjects taking concomitant medications by Anatomical Therapeutic Chemical (ATC) classification level 4 and preferred term. If the ATC level 4 coding is not available for a preferred term, the next available lower level ATC code will be used.

Concomitant medications flagged as anti-COVID-19-drugs will be summarized by treatment and total with their ATC classification showing the number and percentages of subjects stratified by prior use, prior and concomitant use, and concomitant only use. The duration of anti-COVID-19 drug use will be summarized descriptively for the categories prior, prior and concomitant, and concomitant only.

The following by-subject listings will be provided based on the ITT Analysis Set:

- Prior/concomitant medication;
- Use of anti-COVID-19 drugs.

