#### 8.2.1 Reference Dates and Study Day

Reference dates are used to assign study periods relative to IP.

- The reference date for safety, CCI and PK is the start date (and time) of treatment (i.e., the date [and time] of the administration of IP) and will be used to calculate the study day and to assess the baseline value to calculate changes from baseline or shifts to baseline.
- The reference date for efficacy is the date (and time) of randomization and will be used to calculate the time interval for the efficacy time-to-event endpoints and to assess the baseline value to calculate changes from baseline or shifts to baseline.

If the date of interest occurs on or after the reference date, then the study day will be calculated as (date of interest - reference date) + 1. If the date of interest occurs before the reference date, then the study day will be calculated as (date of interest - reference date). There is no study day 0.

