#### **8.2.7.4 Subgroup: Use of Approved / Emergency-authorization Usage of Anti-COVID-19 Drugs**

- Any concomitant usage of anti-COVID-19 drugs during the trial: yes;
- Any concomitant usage of anti-COVID-19 drugs during the trial: no.

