### 10.1.1 Primary Estimand

Clinical question of interest: Is there a treatment benefit of CSL312 after IV infusion in patients with COVID-19, i.e. does treatment with CSL312 + SOC reduce the risk to progress to tracheal intubation or to die prior to tracheal intubation in subjects with severe COVID-19 disease while subjects are treated with SOC?

The primary estimand in line with the primary interest of the study follows the treatment policy strategy and is described as follows:

- A. Subject population: the target subject population defined by eligibility criteria.
- B. Treatment condition of interest: One dose (700 mg) of IP (CSL312 + SOC or Placebo + SOC) via IV infusion on peripheral vein.
- C. Variable: subject’s progression to tracheal intubation or death prior to tracheal intubation at any time from randomization to Day 28.
- D. Intercurrent events:
  - 1. Concomitant use of anti-COVID-19 drugs.
  - 2. Early discontinuation of the study for any reason.
  - 3. Randomized without treatment.
- E. Population level summary: risk difference of progression to tracheal intubation or death prior to tracheal intubation (CSL312 + SOC minus placebo + SOC).

In this study, the treatment policy strategy will be used for all intercurrent events. It is reasonable to assume for subjects who are losses to follow-up after hospital discharge likely not to have experienced the event under randomized treatment. If subjects are still in hospital after withdrawal from the study (but not withdrawal of consent), missing data is unlikely to occur.

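### SAP 9.4 classes every medication of a randomised but untreated subject as 'Prior', so post-randomization drugs drop out of the ITT concomitant-medication table and are labelled prior use in the anti-COVID-19 drug table

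*SAP*

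**What the plan says.** SAP 9.4 sorts each medication into one of three classes.

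- 'Prior' applies "if the subject has not taken any IP; or if the medication end date is before IP start date".
- 'Concomitant Only' applies "if the medication started on or after IP start date".
- 'Prior and Concomitant' is the remainder: whatever fits neither of the other two.

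The SAP then defines concomitant medications as the last two classes only. These "will be summarized for the ITT Analysis Set by treatment and total showing the number and percentage of subjects taking concomitant medications".

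A second table covers anti-COVID-19 drugs: "Concomitant medications flagged as anti-COVID-19-drugs will be summarized by treatment and total with their ATC classification". It is stratified by all three classes, including prior use, and the duration of use is also summarised for all three. By-subject listings on the ITT set cover both prior/concomitant medication and anti-COVID-19 drugs.

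Under SAP 6.2 the ITT set keeps every screened subject with a randomization number, whatever was received. The SAP foresees untreated subjects. They have their own line in the disposition table (9.1), and "Randomized without treatment" is the third intercurrent event in 10.1.1. The first intercurrent event there is use of anti-COVID-19 drugs alongside study treatment.

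**The concern.** The 'Prior' rule attaches no date to subjects without IP, while the rest of the SAP's efficacy framework counts from randomization. SAP 8.2.1 states: "The reference date for efficacy is the date (and time) of randomization". SAP 8.3 starts the Treatment Period at randomization. A drug begun inside the Treatment Period can therefore be tabulated as prior medication, solely because the subject was never dosed.

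What is at stake is the description of background therapy by arm. The primary estimand follows a treatment policy strategy, so a reader needs post-randomization therapy in each ITT arm to interpret the estimate. For subjects with both intercurrent events (no IP, and anti-COVID-19 drug use), SAP 9.4 misreports the second. These are subjects whose background therapy is the only therapy they received.

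**Working it through.** **Step 1: apply the three rules.** Inputs are the class definitions in SAP 9.4. Day 1 is the day of randomization and, for treated subjects, of IP. The last column replaces IP start by randomization for the untreated subject.

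| Record | Class under SAP 9.4 | In ITT concomitant-medication table? | Class if anchored to randomization |
|---|---|---|---|
| Treated Day 1; drug Days 3 to 10 | Concomitant Only | Yes | unchanged |
| Untreated; drug Days 3 to 10 | Prior | No | Concomitant Only |
| Untreated; drug Day -2 to Day 10 | Prior | No | Prior and Concomitant |
| Untreated; drug Day -5 to Day -1 | Prior | No | Prior |
| Treated Day 1; drug Day -5 to Day -1 | Prior | No | unchanged |

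Rows 1 and 2 have the same drug and the same dates. Only the receipt of IP differs, and it moves the record out of the table. No other class is open to the untreated subject: 'Concomitant Only' needs an IP start date, and the remainder class takes only what is not already 'Prior'.

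**Step 2: the anti-COVID-19 table.** Two parts of SAP 9.4 conflict. The lead-in limits the table to concomitant medications, a term just defined without 'Prior'. The strata and the duration summary include prior use. If the printed strata are followed, the records in rows 2 and 3 appear as prior use. If the lead-in is followed strictly, they drop out, and the prior-use stratum is empty for everyone.

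**Step 3: size.** The denominator is the planned arm size of 62 (SAP 4.4). It reproduces from the SAP's rates of 30% and 10%, 1-sided alpha 0.025 and 80% power, using the pooled chi-square formula without continuity correction:

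n = [1.960 × √(2 × 0.20 × 0.80) + 0.842 × √(0.30 × 0.70 + 0.10 × 0.90)]² / 0.20² = (1.109 + 0.461)² / 0.04 ≈ 61.6, so 62 per arm and 124 in total. Power at 62 per arm is 0.803.

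The point does not depend on this calculation; it only supplies the denominator. If u untreated subjects in one arm use a drug after randomization, the arm's percentage is understated by 100 × u / n. The documents give no value for u, so 1 to 5 is an assumption:

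- n = 62: 1/62 = 1.6 points; 5/62 = 8.1 points.
- n = 124 (the SAP's maximum of 248 in total): 1/124 = 0.8 points; 5/124 = 4.0 points.

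With u = 0 there is no effect.

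**Step 4: outputs that use these drugs by another route.** The sensitivity analysis in SAP 10.1.3 counts anti-COVID-19 drugs started after randomization as events, so it does not use the 9.4 classes. An untreated subject who starts such a drug on Day 3 is therefore a post-randomization user in 10.1.3 and a prior user in 9.4. The subgroup in SAP 8.2.7.4 reads "Any concomitant usage of anti-COVID-19 drugs during the trial: yes" and names neither a reference date nor a source section.

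**The case against.** The strongest reply is that little follows from this. IP is a single dose, given on Day 1 by study personnel in hospital (SAP 4 and 10.5), so untreated subjects should be few. Both ITT listings keep every record. All intercurrent events are handled by treatment policy, so the primary analysis never uses the medication class. The one sensitivity analysis on these drugs is anchored to randomization and handles untreated subjects correctly. SAP 10.3 makes every test but one descriptive. All of this stands, and it sets the low weight of the point. It does not cure the general concomitant-medication table, and nothing elsewhere in the SAP gives untreated subjects another reference date.

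A reader might infer two stronger things that the documents do not support.

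- *That these drugs vanish from the anti-COVID-19 table.* That table and its duration summary have a prior category, so mislabelling is the likelier outcome. Loss follows only from the strict reading of the lead-in.
- *That untreated users are filed as non-users in a primary-endpoint subgroup.* This needs the 8.2.7.4 flag to be built from the 9.4 classes, which the SAP does not say. The comorbidity subgroup just before it (8.2.7.3) points to its derivation in 9.3; this one points nowhere. Its reference to use during the trial can be read from randomization, where the Treatment Period starts. The ambiguity is real, because 9.4 is the only place where the SAP defines a concomitant medication, but it is no more than an ambiguity.

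**Conclusion.** The rule is wrong as written for randomised subjects without IP. Their post-randomization medications cannot enter the ITT concomitant-medication table, at a cost of about 1.6 percentage points per untreated user in an arm of 62. In the anti-COVID-19 table the same use is labelled prior, or is dropped on the strict reading.

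The classification follows from the text alone. The total size rests on an unknown number of untreated users, which may be zero; the 1.6 to 8.1 point range assumes 1 to 5 in one arm. No size is given for the subgroup, because the link it needs is not stated. No effect is shown on the primary analysis, on the anti-COVID-19 sensitivity analysis or on the listings. This is a low-severity correction to descriptive tables.

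**What to change.** Make three changes to the SAP.

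1. In 9.4, for ITT subjects who received no IP, use the date and time of randomization in place of IP start in all three class definitions, including the rules for partial dates. 'Prior' then requires an end before randomization, and 'Concomitant Only' a start on or after it. The present no-IP clause should no longer apply to randomised subjects.
2. In 9.4, state whether 'Prior' records enter the anti-COVID-19 drug table and its duration summary, and make the lead-in agree with the strata.
3. In 8.2.7.4, state how the flag is derived and use the same anchor for untreated subjects.

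The cost is a few sentences and a small change to the derivation code. Medication start and end dates are already recorded in the eCRF (protocol 9.1) and the randomization date and time are already used in the SAP, so no new data are needed. The change should be made before unblinding.

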## 10 Efficacy

The randomized treatment will be used for the efficacy analyses described in this section.

## 10.1 Progression to Tracheal Intubation or Death Prior to Tracheal Intubation

Progression to tracheal intubation will be defined as presence of a record for this procedure (“Endotracheal Intubation” ticked on the Respiratory Support CRF) with a start date from randomization to Day 28. All deaths will be reported as SAEs. An SAE with outcome “Death Related to Adverse Event” and SAE end date from randomization to Day 28 will be considered as death for the primary endpoint.

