7.2 Efficacy Assessments

Outcome assessments will include the following:

- Use of supplemental oxygen
- Use of CPAP or BiPAP
- Use of HFNC
- Use of ECMO
- Intubation
- Extubation
- Clinical status on standardized scales (SOFA score and NIAID 8-point ordinal scale score)
- ICU admission and discharge
- Hospital discharge or death

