10.1 Definitions

10.1.1 Adverse Event

As per ICH E2A (Clinical Safety Data Management: Definitions and Standards for Expedited Reporting), an AE is any untoward medical occurrence in a patient or clinical investigation subject administered a pharmaceutical product and which does not necessarily have a causal relationship with this treatment. An AE can, therefore, be any unfavorable and unintended sign (including an abnormal, clinically significant laboratory finding), symptom, or disease temporally associated with the use of a medicinal (investigational) product, whether or not considered related to the medicinal (investigational) product.

The period of observation for AEs extends from the time that informed consent is obtained until the EOS Visit (see [Section 10.4](#) for further details).

Adverse events may include:

- Exacerbation (ie, an increase in the frequency or severity) of a pre-existing condition. Illness present before study entry should be recorded in the medical history section of the eCRF and only be reported as an AE if there is an increase in the frequency or severity of the condition during the study.
- A clinical event occurring after consent but before IP administration.
- Intercurrent illnesses with an onset after administration of IP.

Adverse events do not include:

- Events identified at Screening that meet exclusion criteria.
- Medical or surgical procedures (the condition that leads to the procedure is the AE).
- Situations where an untoward medical occurrence has not taken place. For example:
 - Planned hospitalizations due to pre-existing conditions, which have not worsened.
 - Hospitalizations that occur for procedures not due to an AE (eg, cosmetic surgery).
 - Hospitalizations for a diagnostic procedure where the hospital stay is less than 24 hours in duration or for normal management procedures (eg, chemotherapy).

- Overdose of IP or any concomitant therapy that does not result in any adverse signs or symptoms.

For laboratory safety parameters, any instances of absolute values being outside the reference range or changes at any visit after study start that are considered by the investigator as clinically significant must be recorded in the eCRF as AEs. In addition, at the investigator's discretion, any changes or trends over time in laboratory parameters can be recorded in the eCRF as AEs if such changes or trends are considered to be clinically relevant, even if the absolute values are within the reference range.

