10.4 Observation Period for Adverse Events

The observation period for the reporting of AEs (and SAEs) for an individual subject will start at the time that informed consent is obtained for participation in the current study and end at the subject's final site visit.

If the investigator becomes aware of an SAE that has started after the EOS Visit and is considered by the investigator causally related to the IP, the event must be reported to CSL following the same timelines and procedures described for SAEs occurring during the study (see Section 10.6.1).

Such events are not entered into the eCRF.

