### **10.2 Analysis of Secondary Endpoints**

Secondary Efficacy Endpoints are:

- All-cause mortality: calculated as number of deaths of any cause from randomization to Day 28 divided by the number of subjects in the treatment group. All deaths will be entered as SAEs in the AE CRF. Thus, the information will be obtained from the AE CRF as SAEs with outcome “Death Related to Adverse Event” and SAE end date (death date) occurring within the 28 days of the Treatment Period.
- Incidence of tracheal intubation from randomization to Day 28: calculated as number of subjects experiencing intubation from randomization to Day 28 divided by the number subjects in the treatment group. Tracheal intubation is defined as presence of a record for this procedure (“Endotracheal Intubation” ticked on the Respiratory Support CRF) with a start date during the 28 days of the Treatment Period.
- Proportions of subjects using CPAP or BiPAP: calculated as number of subjects using CPAP or BiPAP within 28 days of randomization divided by the number subjects in the treatment group. Use of CPAP or BiPAP is defined as presence of a record for this procedure (“CPAP” or “BiPAP” ticked on the Respiratory Support CRF) with a start date during the 28 days of the Treatment Period.
- Proportion of subjects using HFNC: calculated as number of subjects using HFNC within 28 days of randomization divided by the number subjects in the treatment group. Use of HFNC is defined as presence of a record for this procedure (“HFNC” ticked on the Respiratory Support CRF) with a start date during the 28 days of the Treatment Period.

- Proportion of subjects using ECMO: calculated as number of subjects using ECMO within 28 days of randomization divided by the number subjects in the treatment group. Use of ECMO is defined as presence of a record for this procedure (“ECMO” ticked on the Respiratory Support CRF) with a start date during the 28 days of the Treatment Period.
- Clinical status assessed on an 8-point NIAID ordinal scale as entered in the CRF.
- Length of hospital stay defined as time interval from randomization to hospital discharge alive. The information will be derived from the SARS-CoV-2 CRF along with the AE CRF for the survival status (no SAE with outcome “Death Related to Adverse Event” reported).
- Subject’s maximum SOFA score, subject’s maximum change from baseline in SOFA score, and subject’s mean SOFA score during the study will be calculated.

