### 11.1 Extent of Exposure

Subjects will receive 1 dose of IP. Duration of exposure is not relevant in this study. Duration of follow-up is of interest as this has an impact on the reporting of efficacy events and AEs.

Duration of follow-up will be descriptively summarized by treatment and total. The duration of follow-up is defined as:

$$\text{Subject's duration of follow-up (days)} = \text{EOS date} - \text{date of randomization} + 1,$$

where EOS date is either Day 28 or withdrawal date for subjects who discontinued.

A summary table will be provided with descriptive statistics as specified in Section 7 for:

- Duration of follow-up [days] per subject;
- Volume [mL] received per subject.

A by-subject listing will be provided based on the Safety Analysis Set including:

- Infusion date, start and end time, and duration (if start and end time is available);
- Volume administered [mL], location of infusion;
- Dose modified with reason.

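### Death is derived only from the adverse-event page, whose reporting window can close at study withdrawal, so a death after withdrawal but by Day 28 can be counted as no event in the primary endpoint and in all-cause mortality

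*SAP*

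**What the plan says.** **Source of death.** SAP 10.1 states that all deaths are reported as SAEs, and that an SAE with the fatal outcome code "and SAE end date from randomization to Day 28 will be considered as death for the primary endpoint". For all-cause mortality, SAP 10.2 says "the information will be obtained from the AE CRF as SAEs with outcome" set to the same code. Death is also collected elsewhere: Protocol 7.2 lists "Hospital discharge or death" among the outcome assessments, and death is category 1 of the NIAID scale (Protocol Appendix 3, SAP 15.3). The SAP uses neither to derive death.

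**When the source closes.** Protocol 10.4 has AE and SAE reporting "end at the subject's final site visit". An SAE starting after the EOS Visit is reported only if judged related to the product, and "Such events are not entered into the eCRF"; Protocol 10.6.2 has the same rule after the final study visit. Protocol 10.1.1 words the window differently: it "extends from the time that informed consent is obtained until the EOS Visit". SAP 8.3 places EOS at Day 28, while SAP 11.1 defines duration of follow-up by an end date, "where EOS date is either Day 28 or withdrawal date for subjects who discontinued".

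**What happens without a record.** SAP 10.1.2 and 10.4 count a subject with under 28 days of follow-up and no documented intubation or death as not having progressed. SAP 10.2.1 applies the same default to the binary secondary endpoints, mortality included.

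**Estimand.** SAP 10.1.1 uses a treatment-policy strategy for all intercurrent events and names early study discontinuation as one. It argues: "If subjects are still in hospital after withdrawal from the study (but not withdrawal of consent), missing data is unlikely to occur". For losses after discharge it assumes that the event probably did not occur.

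**The concern.** A treatment-policy estimand that names early discontinuation needs the outcome to Day 28 whether or not the subject stays in the study. The derivation relies on one page, and for a withdrawn subject the reporting rules can be read as closing that page at withdrawal. An unrelated death the following week would then have no place in the eCRF as an SAE, and the default would score it as a favourable outcome.

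Two endpoints are exposed. In the primary endpoint only deaths without an earlier recorded intubation matter, because an intubated subject is already an event. In all-cause mortality every such death matters. Unequal loss between arms biases the risk difference in either direction; equal proportional loss shrinks it.

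**Working it through.** **1. Tracing three kinds of subject through the rules**

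| Subject | Route by which a death by Day 28 could be recorded | Result under the SAP |
|---|---|---|
| In hospital and in the study | SAE page, entered within 24 hours of awareness (Protocol 10.6.2) | Counted |
| Discharged, consent maintained | In the study to Day 28, with weekly calls covering clinical status and AEs (Protocol 6.4.1) | Counted if a call establishes the death and the site treats the page as open |
| Withdrawn from the study | Attempted Day 28 assessments (Protocol 6.4.4); new SAEs after the last visit entered nowhere in the eCRF | Can default to no event |

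The gap is clearest in the third row. The second row depends on which window a site applies: calls to Day 28 (6.4.1), the EOS Visit (10.1.1) or the last site visit (10.4). For someone who does not come back in person, the last site visit may be the day of discharge.

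The SAP's reassurance about withdrawn subjects still in hospital has the same weakness. The hospital may know of the death, but the analysis reads only the AE page. SAP 10.2.1 also takes survival status for length of stay from that page. A withdrawn inpatient whose death is unrecorded would be censored at discontinuation, not at 28 days as for a recorded death.

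**2. The plan's own sample size**

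Inputs (Protocol 11.1, SAP 4.4): 30% versus 10%, two-sided 0.05 (one-sided 0.025), 80% power, 1:1, chi-square. With pooled variance under the null and mean rate 0.20:

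n per arm = [1.960·√(2·0.20·0.80) + 0.842·√(0.30·0.70 + 0.10·0.90)]² / 0.20² = 61.6, rounded up to 62, total 124.

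This matches the plan; power at 62 per arm is 80.3%. The figure is not in dispute and no new sample size follows.

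**3. Missed deaths near the design rates**

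Expected events: 0.30 × 62 = 18.6 and 0.10 × 62 = 6.2, taken as 19 and 6. The test is an unadjusted pooled z-test, not the planned Firth model: z = (a − b)/62 ÷ √(2·p̄(1 − p̄)/62), with a control events, b CSL312 events and p̄ = (a + b)/124. For 19 versus 6: p̄ = 0.2016, SE = 0.0721, z = 2.91, one-sided p = 0.0018.

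| Control vs CSL312 events | Meaning | Risk difference (points) | One-sided p |
|---|---|---|---|
| 19 vs 6 | Starting point | −21.0 | 0.0018 |
| 17 vs 6 | Two control deaths missed | −17.7 | 0.0055 |
| 15 vs 6 | Four control deaths missed | −14.5 | 0.0156 |
| 14 vs 6 | Five control deaths missed | −12.9 | 0.0254 |
| 19 vs 9 | Truth, if three CSL312 deaths were missed | −16.1 | 0.0159 |
| 19 vs 10 | Truth, if four CSL312 deaths were missed | −14.5 | 0.0281 |

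Closer to the threshold, fewer suffice: 18 versus 8 gives p = 0.0137, 17 versus 8 gives 0.0220 and 16 versus 8 gives 0.0345.

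**4. Operating characteristics under assumed loss rates (62 per arm)**

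- True rates 30% and 10%, with 5%, 10% or 20% of events missed in each arm: the risk difference becomes −19, −18 or −16 points, and power falls from 80.3% to 77.6%, 74.8% or 68.5%.
- No true effect (30% in both arms), with one, two or three expected events missed in the CSL312 arm only: exact one-sided type I error of the unadjusted test rises from 2.5% to 3.9%, 5.9% or 8.7%.

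These loss rates are assumptions. The documents give none, and SAP 10.1.3.1 says only that few missing outcomes are expected.

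**The case against.** The strongest reply is that the SAP requires every death to be reported as an SAE, so a death noted in the outcome assessment should also be on the AE page. Consenting subjects who are discharged stay in the study to Day 28, with weekly calls on clinical status and AEs. The bar on eCRF entry concerns SAEs that start after the EOS Visit. One already running is followed to resolution (Protocol 10.5, 10.6.1), and because the SAP uses the SAE end date, its fatal outcome can still count. The primary endpoint has a missing-as-event analysis, a complete-case analysis and a tipping-point analysis.

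Most of this stands. A reader might infer that every Day 28 death in withdrawn or non-returning subjects is scored as no event, or that deaths known to the site are routinely discarded. The documents do not support either: telephone contact is a working route for discharged subjects, Day 28 assessments are attempted after withdrawal, and loss requires a death never ascertained or a page treated as closed. A reader might also infer that one or two missed deaths would overturn the trial. That holds only for counts already near the threshold.

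The reply does not close the gap for withdrawn subjects. The instruction to report all deaths is in the SAP, whereas sites follow the protocol, whose window may have ended. The sensitivity analyses vary assumptions about a missing outcome; they do not recover a recorded fact. The tipping-point analysis runs only after a significant primary result, so it would not examine a benefit hidden by missed control deaths. None of the three is specified for mortality.

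**Conclusion.** The point holds in a limited form. Under the plan as written, a death after study withdrawal and by Day 28 can be missing from the only source the SAP reads and then be scored as no event, contrary to the treatment-policy estimand. For discharged subjects still in the study the exposure is smaller and comes from three windows that disagree. All-cause mortality is the weaker endpoint: every such death counts there, and no analysis tests the default.

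The effect on the primary result cannot be estimated from the documents. Near the design rates it takes five missed deaths in control, or four in CSL312, all in one arm and none with an earlier recorded intubation, to change significance. Those counts rest on an unadjusted test and illustrate sensitivity; they do not predict what will happen. The change is worth making because it removes an avoidable bias at little cost.

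**What to change.** 1. **SAP 10.1 and 10.2:** derive death from any recorded source (outcome-assessment death record, NIAID category 1, discontinuation or discharge record, telephone contact, SAE page), using date of death on or before Day 28. Use the same variable for survival status in length of stay.
2. **Protocol 10.4, with 10.6.2 aligned:** state that, where consent allows, any death through Day 28 is entered in the eCRF for every randomized subject regardless of withdrawal, last visit or causality.
3. **Reconcile** Protocol 6.4.1, 10.1.1 and 10.4 on when the reporting window ends, and make clear that the withdrawal-based end date in SAP 11.1 does not close collection of deaths.
4. **SAP 10.2.1:** add the missing-as-event analysis for all-cause mortality, mirroring SAP 10.1.3.

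The cost is a revised derivation, a short protocol clarification and one further mortality analysis. No new assessment and no change in sample size are needed.
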